9.4.1 Changes in IL-6

A total sample size of 60 **participants** will be randomized at a 2:1 ratio to ruxolitinib:no study treatment, allowing for 20% lost to follow-up and treatment discontinuation, is anticipated to yield 48 evaluable **participants** (see section 9.6.1). This will provide 80% power to detect a treatment effect of 0.20 log₁₀ pg/mL, that is a difference between treatment groups in (change in plasma IL-6 from entry to week 5), assuming that the standard deviation (SD) of within-**participant** differences in IL-6 is 0.25 log₁₀ pg/mL, using a two-sided t-test at a 0.10 alpha level.

To minimize variability and maximize statistical power, at each key time point markers will be measured and analyzed as the average of samples taken 1-2 weeks apart (pre-entry and entry; at weeks 4 and 5; at weeks 10 and 12).

A5336 FINAL Version 2.0 05/21/15

The treatment effect of 0.20 log₁₀ scale pg/mL corresponds to average decreases of 37% and 0% in plasma IL-6 levels in the ruxolitinib and no study treatment arms, respectively. This choice of effect size is based on prior data examining plasma IL-6 levels in HIV-1 infected populations and changes in IL-6 levels in ruxolitinib treated populations. Specifically, a 27% (95% confidence interval [CI]: 11% to 39%) reduction in IL-6 levels after 4 weeks and a 37% (95% CI: 13% to 53%) reduction after 24 weeks of treatment was seen in the Phase III COMFORT-1 study [3]. The effect size of 37% is selected because it is contained in the 95% CI for IL-6 reduction at 4 weeks, and balances the interest in the efficacy endpoint with safety considerations as well as feasibility for this early phase investigation of the effects of the study treatment in the HIV-1 population.

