## 2 Study Overview

### 2.1 Design

A5336 is a multi-center, randomized, open-label, two-arm, phase IIa study. Eligible participants on approved ART with virologic suppression will be randomized to receive ruxolitinib or no study treatment to measure safety and tolerability and to determine whether there are changes in systemic immune activation and inflammation after 5 weeks of treatment with ruxolitinib.

A total of 60 participants will be randomized 2:1 to ruxolitinib or no study treatment; 40 on ruxolitinib and 20 on no study treatment. The study aims to enroll at least 15 participants on efavirenz (EFV) in order to have at least 8 ruxolitinib-treated participants to evaluate pharmacokinetic (PK) interactions with Efv.

The study population consists of HIV-1 infected males and females  $\geq 18$  and  $< 75$  years of age on stable ART for at least 12 weeks prior to study entry containing TDF/FTC, TAF/FTC, TDF/3TC, or ABC/3TC, plus a NNRTI or INSTI (not containing cobicistat) who:

- Are on ART for at least 2 years
- Have virologic suppression (see protocol for definition)
- Have CD4+ T cell count  $> 350$  cells/mm^3 within 45 days prior to study entry
- Have no medical conditions, or concomitant medications, prohibiting the use of janus activating kinase-signal transducer and activator of transcription (Jak-STAT) inhibitor

All participants will be followed for up to 12 weeks after randomization. Participants randomized to the ruxolitinib arm will receive 10 mg of ruxolitinib orally twice daily for 5 weeks and then will be followed off-treatment for an additional 7 weeks.

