  - Confirmed HIV-1 RNA level above the lower limit of quantification in the absence of an interruption in ART.
  - New or recurrent CDC category C AIDS-indicator condition.
  - HIV-1 associated infection including Herpes zoster.
  - Lymphoproliferative malignancies.
  - Occurrence of Grade 2 or higher thrombocytopenia.
  - Grade 4 or recurrence of Grade 3 anemia/neutropenia.
  - Any Grade 4 or recurrence of Grade 3 toxicity.
  - New diagnosis of pneumonia, sepsis, or bacteremia.
- 4) Occurrence of protocol-defined reportable adverse events (all diagnoses, Grade 3 or higher sign/symptoms or laboratory values, any signs/symptoms or laboratory values that led to a change in treatment or met ICH, EAE, or SAE guidelines) at any post-entry time point.
- 5) Safety Laboratory values (estimated creatinine clearance, creatinine, AST (SGOT), ALT (SGPT), ANC, hemoglobin, platelet count) across all study weeks (at entry, week 1, and week 2, and arithmetic means at weeks 4 and 5, and at weeks 10 and 12).
- 6) Change in safety laboratory values (estimated creatinine clearance, creatinine, AST (SGOT), ALT (SGPT), ANC, hemoglobin, and platelet count) across all study weeks (at weeks 1 and 2, and arithmetic means at weeks 4 and 5 and at weeks 10 and 12).
- 7) Change in log10-transformed plasma IL-6 across all study weeks (geometric means of pre-entry and entry, and week 10 and 12).
- 8) Changes in soluble markers of immune activation and inflammation in the peripheral blood (sCD14, TNF- $\alpha$ , IL-1 $\alpha$ , IL-1 $\beta$ , IL-7, IL-10, IP-10, IL-18, mCSF, and neopterin) across study weeks from baseline (geometric mean of pre-entry and entry) to week 4/5 (geometric mean of week 4 and week 5) and week 12.

- 9) Changes in cellular markers of immune activation and inflammation in the peripheral blood (HLA-DR, CD25, CD38, CD69, CD127, Ki67, BCL2, a4b7, CX3CR1, PAR-1 measured on CD4 and CD8 cells; monocyte subsets (classical, inflammatory, and patrolling) defined by CD14 and CD16 expression; proportion of monocyte subsets (classical, inflammatory, and patrolling) expressing CCR2, CX3CR1, and CD163) from entry to weeks 5 and 12.
- 10) Level of plasma HIV-1 RNA at baseline and weeks 2, 5, and 12.
- 11) Change in CD4+ T cell counts from baseline (mean of pre-entry and entry) to weeks 2, 5, and 12.
- 12) Changes in HIV-1 reservoir (HIV-1 RNA by SCA, cellular HIV-1 total RNA and DNA) from entry to weeks 5 and 12.

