### 3 General Analysis Considerations

Study entry is defined as the date of the entry visit recorded on study initiation case report form.

The protocol-defined study week windows are modified for analysis purposes. For all analyses, the following window definitions will be used:

Pre-entry:	The last visit that occurred at least 24 hours prior to entry, but not more than 7 days before
Entry:	The visit after randomization, and prior to initiation of study treatment: Days [0-3]
Week 1:	The first visit in the window: Days [4, 22]
Week 2:	The second visit in the window: Days [4, 22]
Week 4:	The first visit in the window: Days [25, 39]
Week 5:	The second visit in the window: Days [25, 39]
Week 10:	The first visit in the window: Days [56, 93]
Week 12:	The second visit in the window: Days [56, 93]

Baseline values are the average of pre-entry and entry values, the week 4/5 values are the average of week 4 and week 5 values, and the week 10/12 values are the average of week 10

and 12 values; averages will be calculated using geometric means for log-transformed data and arithmetic mean for non-transformed data. If missing one of the pre-entry or entry values, then the available measure will be used as the baseline value, and similarly, if missing one of the week 4 or week 5 values or week 10 or week 12 values, then the available measure will be used as the week 4/5 value or week 10/12 value, respectively.

Analyses will be done among those in the as-treated population or among those in the safety analysis population (Cameron 2008), depending on the outcome; see the Statistical Methods section for details on populations for specific outcomes. The safety analysis population will consist of all participants randomized to the no-treatment arm and all participants who took at least one dose of ruxolitinib among those randomized to the ruxolitinib arm. The as-treated population is defined as participants who meet the following conditions: (1) have data at baseline and week 4/5, (2) for the ruxolitinib arm, remained on study treatment through week 4/5 and missed no more than 6 doses cumulatively, (3) did not change ART, use prohibited medications, or had confirmed virologic failure in this time period. Participants found to be ineligible after enrollment will be included in all safety analyses, but excluded from other analyses.

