#### **4.2.4 HIV-1 Reservoir**

Tabular summaries of categorized HIV-1 RNA by iSCA (secondary outcome 12) will be provided by study week and arm. To compare changes in iSCA over time and between study arms, a GEE model for binary data will be used since it is anticipated that a substantial proportion of the data will be below assay limit (Riddler 2016).

Total HIV-1 DNA and cell-associated HIV-1 RNA will be log-10 transformed and summarized by arm and across study weeks with continuous summary statistics and longitudinal plots, imputing values below the assay limit as the lower limit of the assay; as with the immunology markers, results will be back-transformed to fold-changes for presentation. Total HIV-1 DNA and cell-associated HIV-RNA will also be summarized categorically as the frequency and percent below or above the lower limit; if there are differential assay lower limits, an analytic lower limit will be applied for this summary.

Results below assay limit are not anticipated for total HIV-1 DNA (Gandhi 2017). Changes from baseline will be contrasted between study arms using a two-sided t-test with 10% alpha at each visit (week 5 and week 12); in addition, a comparison between week 5 (end of treatment) and week 12 (end of study) will also be done.

Modest amounts of below assay limit observations are anticipated for cell-associated HIV-1 RNA (Gandhi 2017). To contrast changes over time between study arms, a longitudinal censored normal model approach will be used, which was developed for below assay limit HIV virology data and can handle different assay limits (Riddler 2016, Vaida 2009).

In the event that a large proportion of participants have values below assay limits for total HIV-1 DNA and cell-associated HIV-1 RNA, a binary analysis approach similar to the analysis of iSCA will be used.

All analyses will occur in the as-treated population. For GEE and longitudinal censored normal models, the analysis will also be restricted to those who have results for corresponding time points of interest.

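### SAP 4.2.4 limits the reservoir models to participants with results at undefined time points, so the censored-normal model loses partial data it could use (minor)

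*SAP*

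**What the plan says.** The reservoir outcomes are secondary: "Changes in HIV-1 reservoir (HIV-1 RNA by SCA, cellular HIV-1 total RNA and DNA) from entry to weeks 5 and 12" (SAP 2.4.2). The schedule of events (Protocol 6.1) collects the reservoir and single-copy samples at entry, week 5 and week 12, plus any premature discontinuation visit. There is no pre-entry or week 4 sample to stand in for a missing one.

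SAP 4.2.4 assigns the methods:

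- Single-copy RNA: "a GEE model for binary data will be used".
- Cell-associated RNA: "a longitudinal censored normal model approach will be used", chosen to handle values below the assay limit.
- Total DNA: two-sided t-tests on change at week 5 and at week 12, and a comparison of week 5 with week 12. The binary approach is the fallback if many DNA or cell-associated RNA values fall below the limit.

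On the analysis set it states "All analyses will occur in the as-treated population". Section 3 defines that population partly by the condition "1) have data at baseline and week 4/5", without naming a marker. For the GEE and censored-normal models, 4.2.4 then adds that "the analysis will also be restricted to those who have results for corresponding time points of interest". It gives no reason, no missing-data assumption and no fit to all available data.

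**The concern.** A likelihood-based longitudinal model can use participants with incomplete follow-up and is valid if data are missing at random. A participant with entry and week 5 results but no week 12 result still informs the entry and week 5 means and, through the within-person correlation, the week 12 mean. Excluding that participant loses the information. It also makes the fit a complete-case one, which generally needs missingness to be unrelated to the outcome within arm.

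The rule also sits oddly with the rest of the SAP. Section 3 accepts a single measurement when one of a pair is missing, 4.2.3 averages whatever is available, and 4.2.5 takes everyone with a specimen. The model best equipped for incomplete data gets the stricter rule. At stake is some precision, and some robustness to missing data, for cell-associated RNA in a sample of about 32 versus 16.

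**Working it through.** **The plan's own figures.** The documents give no sample size or power for the reservoir models. The nearest anchor is the IL-6 calculation in Protocol 9.4.1 and the paragraph that follows it.

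- Evaluable number: the plan, "allowing for 20% lost to follow-up and treatment discontinuation, is anticipated to yield 48 evaluable". 60 × (1 − 0.20) = 48. Allocation is 2:1 ("40 on ruxolitinib and 20 on no study treatment"), so 32 and 16.
- SD of change: 0.306 × √(2 × (1 − 0.68)) = 0.2448, as printed.
- Power with 16 versus 32, difference 0.20, SD 0.25, two-sided alpha 0.10: 82.4% by noncentral t, against 80% stated.

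**Inputs for the check.**

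- Three visits (entry, week 5, week 12) with equal variance and equal correlation r = 0.68. This is the IL-6 value in the protocol, borrowed because none is given for reservoir markers.
- Missing rates by visit are assumptions: 0–10% at week 5, 5–20% at week 12, none at entry, the same in both arms and independent between visits.
- Data are treated as uncensored normal and missing at random.

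**Method.** For each pattern of observed visits, add n × (inverse covariance of the observed visits) to the information matrix of the arm. Invert it, take the variance of the contrast and sum over arms. Compare three sets: all available results, only those with both visits of the contrast (pairwise), and only those with all three visits. The SD and the arm sizes cancel from the ratios; r and the missing rates remain.

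**Worked case: only week 12 missing, fraction c observed.** Let s² be the variance and n the arm size.

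- Entry to week 12, pairs only: variance 2(1 − r)s²/(cn).
- Entry to week 12, all available: variance (s²/n) × [(1 − r)(1 + 2r)/((1 + r)c) + (1 − r)/(1 + r)].
- Squared SE ratio: 2(1 + r)/(1 + 2r + c).
- With c = 0.90: 3.36/3.26 = 1.0307, square root 1.015, so 1.5% larger. With c = 0.80: 3.36/3.16 = 1.0633, square root 1.031, so 3.1%.
- Entry to week 5: the pairwise rule loses nothing. The all-visits rule gives 1/√c, which is 1.054 at c = 0.90 and 1.118 at c = 0.80.

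The borrowed correlation matters little in this case. At c = 0.80, r = 0 gives √(2/1.8) = 1.054 and r = 1 gives √(4/3.8) = 1.026.

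**Results: increase in SE relative to using all available results.** Each cell lists entry-to-5, entry-to-12 and 5-to-12.

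| Missing at week 5 / week 12 | With all three visits, of 48 | Pairwise rule | All-visits rule |
|---|---|---|---|
| 0% / 5% | 45.6 | 0.0, 0.8, 0.8% | 2.6, 0.8, 0.8% |
| 0% / 10% | 43.2 | 0.0, 1.5, 1.5% | 5.4, 1.5, 1.5% |
| 0% / 20% | 38.4 | 0.0, 3.1, 3.1% | 11.8, 3.1, 3.1% |
| 5% / 5% | 43.3 | 0.7, 0.7, 1.6% | 3.4, 3.4, 1.6% |
| 10% / 10% | 38.9 | 1.5, 1.5, 3.3% | 6.9, 6.9, 3.3% |
| 10% / 20% | 34.6 | 1.4, 3.0, 5.1% | 13.3, 8.5, 5.1% |

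The ranges are 0–5.1% for the pairwise rule and 0.8–13.3% for the all-visits rule.

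**The case against.** The strongest defence is that the SAP speaks of corresponding time points, which fits a contrast-by-contrast rule. The total DNA t-tests in the same section use only participants with both visits of each contrast, so the rule may simply align the model analyses with them. That reading is plausible, and on it the cost is small. The Analysis Implementation Plan, which holds further specifications, is redacted and may define the phrase.

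It is also fair that the 48 are already net of 20% loss and that the as-treated set already needs baseline and week 4/5 data. Most further loss would therefore fall at week 12. That condition names no marker, however, and single-value substitution lets pre-entry and week 4 values satisfy it, so a missing or failed reservoir sample at entry or week 5 remains possible.

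For the GEE the defence largely succeeds. Unweighted GEE generally needs data missing completely at random even when every result is used, and keeping the same people across a change contrast is a defensible choice.

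Some stronger inferences are tempting but not supported:

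- **That the SAP requires results at every visit.** It does not say so.
- **That values below the assay limit are thrown out.** They are results and stay in.
- **That the loss is 1/√(fraction retained) for every contrast.** With 10% missing at both post-entry visits this gives 1/√0.81 = 1.11, or 11%, against 3.3–6.9% in the table. A participant who lacks a visit in the contrast carries only part of the information.
- **That the rule selects differently by arm because the trial is open-label.** The documents offer no mechanism or figure for differential loss of stored-sample results beyond the as-treated restriction, which is a separate matter.

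**Conclusion.** The point holds for the censored-normal model of cell-associated RNA. Under either reading, the rule can remove partly observed participants whom the model could use under missing at random, and no reason is given in 4.2.4. Under the assumed missing rates, standard errors are about 0–5% larger on the pairwise reading and about 1–13% larger if all three visits are required. These figures rest on the borrowed IL-6 correlation and on uncensored normal data; censoring and the binary GEE were not modelled. For the GEE, using all results offers at most a precision gain.

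Severity is minor. The outcomes are secondary in a pilot study, Protocol 6.3.18 and 6.3.19 make the assays conditional on immunologic changes or advances in the field, and the primary safety, tolerability and IL-6 results are unaffected.

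**What to change.** - **Censored-normal model:** remove the restriction, include every as-treated participant with at least one result, and take the week 5, week 12 and week 5-to-12 contrasts from the fitted model. State the missing-at-random assumption and keep the restricted fit as a sensitivity analysis.
- **Binary GEE:** report an all-available-data fit alongside the restricted one, and state that both rest on data missing completely at random.
- **Wherever the restriction stays:** say whether it means all three visits or the two visits in each contrast.

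The cost is a short text edit, one extra fit per model and no new data. The downside is that slightly different participants contribute at different visits, which the restricted fit lets a reader check.

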#### 4.2.5 CMV Co-Infection

Level of CMV shedding (secondary outcome 13), will be summarized by study week and arm as the frequency and percentage of those above and below the assay limit of detection. The proportion of participants with detectable CMV at any on-treatment time point (ever shedding at weeks 1, 2, 4, or 5) and any post-treatment time point (ever shedding at weeks 10 or 12) will be contrasted between study arms via using a two-sided mid-p Fisher's exact test with 10% type-I error.

This analysis will include all participants with available specimen.

### 5 Key Report Elements

In addition to the previously mentioned primary and secondary analyses, the following elements will be included in the final analysis report:

- CONSORT diagram
- Description of ineligible enrollments
- Screen failure rates with reasons
- Accrual by month, site, and stratification factors
- Baseline Characteristics
- Study/Treatment Status
- Duration of Follow-up
- ARV Regimen Status
- ART Adherence
- Concomitant Medication Use
- Additional safety summaries including EAEs, SAEs, deaths, and pregnancies

Detailed descriptions of these elements are provided in the AIP in **Appendix 2**.

### 6 Core Manuscript Writing Team

Redacted.

## **Appendix 1: Analysis Timeline**

Redacted.

## **Appendix 2: Analysis Implementation Plan (AIP)**

Redacted.
